4.6 Changes to Analysis from Protocol

Per protocol, the variable “reason for VKA switch will be described under the OAC treatment management outcome. Finally, reason for VKA treatment switch has not been collected specifically in the VKA section of the CRF. This has been deleted from section 14.2.2 of SAP.

New analysis not included in the final protocol have been considered:

- Antiplatelet treatment according to current NOAC type
- Treatment received at the moment of thromboembolic and bleeding events.
- For all NOACs, the different doses that patients take according to HAS-BLED score.
- Underdosed and overdosed patients (for current NOAC treatment).
- HAS-BLED total score according to NOAC and antiplatelet current treatment.
- Multivariate model to evaluate the association between the Clinical Frailty Scale (dependent variable) and the thromboembolic and the bleeding events (independent variables). To calculate this analysis, only events that have occurred subsequent to the start of anticoagulant therapy (not those prior to the start of VKA / NOACs) will be considered. Univariate analysis will be performed. All variables which have a P value of less than 0.1 will be included in the multivariate analysis.

Document:	H:\HOR-Europe\2019\2512352 - Study on anticoagulation management - BI\Proyecto\Estadistica\SAP\S		
	AP_REBELD_version1.0_08072020.docx		
Author:	██████████	Version Number:	Version 1.0
		Version Date:	[08072020]

Template No.: RWI_TP_BIOS0013 Revision 1

Reference: RWI_WI_BIOS0015

Effective Date: 15Jun2018

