7.2.3 Charlson Comorbidity Index

The Charlson Comorbidity Index (CCI) predicts the ten-year mortality for patients presenting one or more of the conditions in the model, where the age groups and each condition are awarded a specific number of points, some conditions weighing more than others, based on the adjusted risk of mortality. The more points given, the more likely the predicted adverse outcome. The index then sums the points and offers a 10-year survival/ mortality prognosis.

[https://www.thecalculator.co/health/Charlson-Comorbidity-Index-\(CCI\)-Calculator-765.html](https://www.thecalculator.co/health/Charlson-Comorbidity-Index-(CCI)-Calculator-765.html)

<https://www.mdcalc.com/charlson-comorbidity-index-cci>

Document:	H:\HOR-Europe\2019\2512352 - Study on anticoagulation management - BI\Proyecto\Estadistica\SAP\S		
	AP_REBELD_version1.0_08072020.docx		
Author:	██████████	Version Number:	Version 1.0
		Version Date:	[08072020]

Template No.: RWI_TP_BIOS0013 Revision 1

Reference: RWI_WI_BIOS0015

Effective Date: 15Jun2018

Each of the conditions listed below are awarded 1, 2, 3 or 6 points depending on the mortality risk. CCI will be calculated as the sum of all points included in the following table:

Table 2. Point assigned to Charlson Comorbidity Index

	POINTS
Age	
50–59 years	+1
60–69 years	+2
70–79 years	+3
>=80 years	+4
Myocardial infarction	+1
Congestive Heart Failure (CHF)	+1
Peripheral vascular disease	+1
Cerebrovascular Accident or Transient ischemic attack	+1
COPD	+1
Connective tissue disease	+1
Peptic ulcer disease	+1
Liver disease	
Mild	+1
Moderate to severe	+3
Diabetes mellitus	
Uncomplicated	+1
End-organ damage	+2
Hemiplegia	+2
Moderate to severe* Chronic Kidney Disease (CKD)	+2
Solid tumor	
Localized	+2
Metastatic	+6
Leukemia	+2
Lymphoma	+2
AIDS	+6

Document: H:\HOR-Europe\2019\2512352 - Study on anticoagulation management - BI\Proyecto\Estadística\SAP\SAP_REBELD_version1.0_08072020.docx

Author: [REDACTED] Version Number: Version 1.0
Version Date: [08072020]

Template No.: RWI_TP_BIOS0013 Revision 1

Reference: RWI_WI_BIOS0015

Effective Date: 15Jun2018

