Comorbidities and Clinical Risk Factors: - Heart Failure (Yes/No, New York Heart Association (NYHA) classification; Left Ventricular Ejection Fraction, LVEF, %) - Coronary artery disease (Yes/No) - Sleep apnoea-hypopnoea syndrome (SAHS) (Yes/No) - Hypertension (Yes/No) -Hyperlipidemia (Yes/No) - Comorbidity Charlson index (Yes/No; total score): myocardial infarction (already collected for history of thromboembolic events), congestive heart failure (already collected for the NYHA scale scoring), cerebral and peripheral vascular disease, dementia, chronic obstructive pulmonary disease, connective tissue disease, peptic ulcer disease, mild/moderate/severe liver disease, diabetes, diabetes with end-organ damage, hemiplegia, moderate/severe renal disease, any solid tumor, metastatic solid tumor, leukemia, lymphoma AIDs, age (already collected as a demographic characteristic). -History of thromboembolic events (Yes/No, number and date): TIA, ischemic stroke, hemorrhagic stroke, embolism systemic, deep vein thrombosis, pulmonary embolism, stable angina, unstable angina, myocardial infarction with/without ST segment elevation; and bleeding events (Yes/No, number and date): intracranial, digestive, genitourinary, gingival, nasal, pulmonary, articular-muscular, conjunctival.	x	x (NYHA classification, Charlson Index)
CHA2DS2-VASc (total score)		x
HAS-BLED (total score)		x
Clinical Frailty Scale		x
Previous vitamin K antagonist (VKA) treatment (yes/no), type (acenocoumarol or warfarin), start date and treatment duration		
Other concomitant treatments (Total number of current concomitant drugs; Type (Yes/No, number): ARB or ACE inhibitor, Beta-blocker, Calcium channel blockers, Diuretics, Amiodarone, Statin, Proton pump inhibitor, H2-receptor antagonist, Digoxin, NSAIDs, Dronedarone, Other antiarrhythmics, ketoconazole (systemic), cyclosporine, itraconazole	x	

Document: H:\HOR-Europe\2019\2512352 - Study on anticoagulation management - BI\Proyecto\Estadística\SAP\S AP_REBELD_version1.0_08072020.docx

Author: [REDACTED] Version Number: Version 1.0
Version Date: [08072020]

Template No.: RWI_TP_BIOS0013 Revision 1

Reference: RWI_WI_BIOS0015

Effective Date: 15Jun2018

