14.6 Exploratory analysis

History and current antiplatelet treatment will be described by current NOAC type.

Treatment received at the time of thromboembolic and bleeding events will be described, including NOAC, VKA and antiplatelet treatments.

Doses of current NOAC treatment received by the patient will be described according to HAS-BLED score (as low, intermediate and high risk).

The percentage of underdosed and overdosed patients for current NOAC treatment will be described.

HAS-BLED total score (as <3 , $3-5$, ≥ 5) will be described according to NOAC and antiplatelet current treatment.

Multivariate logistic regression will be used to evaluate the association between the Clinical Frailty Scale (dependent variable: Frailty patients - CFS scoring >4 vs Non-frailty patients - CFS scoring ≤ 4) and the thromboembolic and the bleeding events (independent variables). To calculate this analysis, only events that have occurred subsequent to the start of anticoagulant therapy (not those prior to the start of VKA / NOACs) will be considered. Other factors will be age, sex, BMI, smoking habit, alcohol consumption, time since NVAf diagnosis, NVAf type, modified EHRA scale, procedures and interventions, comorbidity Charlson index and clinical risk factors. Univariate analysis will be performed. All variables which have a P value of less than 0.1 will be included in the multivariate analysis.

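### The exploratory frailty regression counts events after the start of anticoagulation but has no covariate for how long each patient has been anticoagulated

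*SAP*

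**What the plan says.** SAP 4.6 lists, among analyses added after the protocol, a "Multivariate model to evaluate the association between the Clinical Frailty Scale (dependent variable) and the thromboembolic and the bleeding events (independent variables"). SAP 14.6 makes it a logistic model of CFS above 4 against 4 or below, and limits the exposure to "only events that have occurred subsequent to the start of anticoagulant therapy (not those prior to the start of VKA / NOACs").

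The adjustment set is given in two parts: "Other factors will be age, sex, BMI, smoking habit, alcohol consumption, time since NVAf diagnosis, NVAf type, modified EHRA scale, procedures and interventions", then "comorbidity Charlson index and clinical risk factors". Selection is by univariate screen: "All variables which have a P value of less than 0.1 will be included in the multivariate analysis". No covariate is forced in. No duration of anticoagulation, VKA duration, NOAC time or offset is listed.

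The data for such a term exist. SAP Table 3 (section 11) lists "Previous vitamin K antagonist (VKA) treatment (yes/no), type (acenocoumarol or warfarin), start date and treatment duration" and dates for thromboembolic and bleeding events. SAP 7.2.7 uses the first NOAC date. Section 6.2 requires NOAC treatment to have begun at least three months before the visit and sets no maximum.

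**The concern.** A patient anticoagulated for three months has had little opportunity for an on-treatment event; one anticoagulated for ten years has had forty times as long. The event term therefore carries information about time observed. If frailty also varies with years on anticoagulant, after the other covariates, the event odds ratio absorbs part of that relation. Table 53 could then show an association between events and frailty that comes only from unequal observation time.

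The spread is wide by the plan's own account. Mock Table 40 foresees NOAC time from under one to over three years, before any VKA time. SAP 8.5 and 14.2 stratify secondary outcomes by time since first NOAC, yet the study's only regression omits it.

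A smaller point concerns patients whose only events came before anticoagulation. SAP 14.6 neither excludes them nor gives them a category, and the primary/secondary prevention split in 14.3.4 shows that such patients are expected.

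**Working it through.** **Plan's own figure.** None exists for this model: no event count, effect size or power is stated. The only planning figures are the Clopper-Pearson widths at N = 500 in Protocol Table 4. They reproduce within rounding (5.46% at 10% prevalence, 8.94% at 50%) and play no part here.

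**Step 1: how the event indicator depends on the window.** P(at least one event) = 1 − exp(−rate × T). The rates are assumed.

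| Rate per year | T = 0.25 y | 1 y | 5 y | 10 y |
|---|---|---|---|---|
| 2% | 0.5% | 2.0% | 9.5% | 18.1% |
| 5% | 1.2% | 4.9% | 22.1% | 39.3% |
| 8% | 2.0% | 7.7% | 33.0% | 55.1% |

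**Step 2: effect on the odds ratio when the truth is 1.** Large-sample simulation, 400,000 patients per scenario. Assumed inputs:
- years anticoagulated: 0.25 plus a gamma variable (shape 1.5, scale 2.5), mean 4
- event rate: 3% or 6% per year
- gap from diagnosis to anticoagulation: exponential, mean 1 or 4 years
- frailty odds ratio per anticoagulated year: as in the first column

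| Frailty OR per year | No time term | Plus time since diagnosis, 1-year gap | Plus time since diagnosis, 4-year gap | Plus time since first anticoagulant |
|---|---|---|---|---|
| 1.05 | 1.11–1.13 | 1.00 | 1.08 | 0.98–1.00 |
| 1.10 | 1.24–1.27 | 1.00–1.02 | 1.14–1.16 | 0.98–1.00 |
| 1.20 | 1.53–1.56 | 1.05–1.07 | 1.32–1.35 | 1.00–1.03 |

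The fits in the last column also held a comorbidity score that was independent of the event.

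A second set used windows up to 6 or 10 years, 3 to 6 events per 100 patient-years and frailty log-odds rising 0.05 to 0.15 per year (odds ratios 1.05 to 1.16):
- no time term: 1.03–1.31
- time since diagnosis, 1-year gap: 0.99–1.06
- time since diagnosis, 4-year gap: 1.04–1.21
- time since first anticoagulant: 0.98–1.03

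**Step 3: with the screen as written.** With n = 500, the same windows and slopes, 4.5 events per 100 patient-years and time since diagnosis kept only if univariate P < 0.1, the mean null odds ratio was 1.01–1.04 (1-year gap) and 1.04–1.19 (4-year gap).

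**Step 4: patients with only earlier events.** Suppose earlier and on-treatment events each have a true odds ratio of 2.0. If 10–30% have earlier events, independent of later ones and multiplying in effect, the fitted odds ratio is 1.93–1.97.

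Suppose instead that earlier events occur only in the reference group, with 25% frailty without events. The event group's frailty is (2 × 1/3)/(1 + 2 × 1/3) = 0.40. A reference group with 20% earlier events has frailty 0.8 × 0.25 + 0.2 × 0.40 = 0.28, so the odds ratio is (0.40/0.60)/(0.28/0.72) = 1.71. At 10% and 30% it is 1.85 and 1.59.

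If a second event adds nothing to frailty and 15–25% have earlier events, it is about 1.64–1.82. A positive correlation between earlier and later events pushes it upward.

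**The case against.** **Time since diagnosis is already a candidate.** This largely stands where treatment followed diagnosis promptly: the bias is then at most about 7%. It fails where the gap is long. SAP 7.2.8 derives the interval from diagnosis to first NOAC as a quantity to be described, so the plan does not assume it short. The screen can also remove the proxy.

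**Age is a candidate too, and frailty need not rise with years on treatment.** Both true. The simulations omit age. If frailty is unrelated to anticoagulated time after adjustment, there is no bias; if longer-treated patients are fitter, it runs below 1.

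**The bias is small beside sampling error.** With 500 patients, 8% with events and 30% frail (assumed), an odds ratio of 2.0 has a 95% interval of about 1.04 to 3.84. This argues against alarm, but a systematic error removable with one covariate is still worth removing.

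**It is exploratory.** The model feeds no primary or secondary objective, which limits the priority. SAP 8.2 and 8.3, which say no testing or modelling will be done, contradict 14.6 more plainly; that is a separate matter.

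**On earlier events, a reader might infer that the plan sets them to no event, and that two opposing biases make the odds ratio uninterpretable.** The documents do not support this. SAP 14.6 is silent on coding; joining those without a counted event is only the default consequence. The restriction to on-treatment events is deliberate and disclosed in 4.6, and for that question a patient with only an earlier event had no on-treatment event. Neither size nor direction of the second effect is fixed.

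Other candidates may carry some of this history. The Charlson index scores "Cerebrovascular Accident or Transient ischemic attack" and myocardial infarction without a date limit (SAP 7.2.3). SAP Table 3 places event history among clinical risk factors, though mock Table 11 omits it. Charlson is an imperfect remedy: it also scores on-treatment strokes, which are the exposure. In the independent scenario of Step 4 it lowered the odds ratio to 1.55–1.63 against a true 2.0.

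**Conclusion.** The main point holds. The exposure accrues over an unlimited and unequal window, and the covariate list has no term for that window. Time since NVAF diagnosis is a partial proxy that the screen can discard.

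Under the assumed inputs, with time since diagnosis in play, the null odds ratio is about 1.0–1.07 for a gap near one year. It is about 1.04–1.2 for a mean gap of four years, rising to about 1.33 if frailty odds increase 20% per anticoagulated year. These figures isolate the time mechanism; they do not predict the study's result, and they require frailty to rise with anticoagulated time.

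The coding of patients with only earlier events is a secondary gap in specification. Its effect may be small and cannot be signed from the documents. The odds ratio remains interpretable as an exploratory estimate with a possible bias of this order. The change should be made; nothing in the primary or secondary analyses depends on it.

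**What to change.** In SAP 14.6 and the Table 53 footnote, state that time from the first VKA or NOAC start to the study visit enters the model with the event terms and is exempt from the P < 0.1 screen.

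The cost is one degree of freedom and some collinearity with time since diagnosis. Under the Step 2 inputs, anticoagulated time has variance 1.5 × 2.5² = 9.375 and the gap has variance 1 or 16. The variance inflation between the two times is 1 + 9.375/1 = 10.4 for the short gap and 1 + 9.375/16 = 1.6 for the long gap. It is therefore modest where the proxy is poor. The inflation falls on the two time coefficients, which are not the target.

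Secondly, state how patients with only pre-anticoagulation events are coded. For one composite thromboembolic and one composite bleeding term, use three levels (none, before only, after start), or add a prior-event indicator to each. This costs two further degrees of freedom. It should not be applied to each of the 10 thromboembolic and 8 bleeding types in mock Tables 13 and 14, which would add up to 18 parameters. SAP Table 3 and section 7.2.7 already provide the dates, so no new data collection is needed.

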9. RESEARCH METHODS

9.1 STUDY DESIGN

This is an observational, multicenter and cross-sectional study in NVAF elderly patients currently on NOAC treatment for their stroke prevention.

AF is classified as non-valvular AF in the absence of mitral stenosis or cardiac valvular prosthesis, since NOACs are not recommended for patients with mechanical heart valve (level of evidence B) or moderate to severe mitral stenosis (level of evidence C) ([22](#)).

The study will be conducted in approximately 50 sites in Spain. Investigators from different specialties are planned to be included as follows: 35 cardiologists, 10 hematologists and 5 geriatricians.

The design of the study impose a single visit to be performed for the informed consent signature and data collection that will coincide with one of those performed by the patients as part of routine follow-up of their disease, without interfering with usual clinical practice of the investigator.

A specific therapeutic strategy has already been assigned to each included patient, based on routine practice and without interference with the physician's prescription habits. The observational nature of the study is ensured as no diagnostic or therapeutic intervention outside of routine clinical practice will be applied.

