9.2.1 Study sites

Cardiology, hematology, geriatric services at a hospital setting, specialty medical offices and nursing homes, who regularly prescribe NOACs for stroke prevention in NVAF patients may be invited to participate.

It is necessary to ensure that study population is representative of the entire national territory. Therefore, patients may be recruited from sites with different level of medical care (e.g, primary hospital, secondary hospital, private care) in several geographical areas according to

the distribution of the overall population in this area. Site selection will be performed in order to secure representativeness of the NVAF population treated with NOAC.

As a pre-study activity, sites will need to answer a site feasibility questionnaire in order to determine that the site has adequate facilities and investigator is qualified and meets the needs of the study, recruitment targets, quality and timelines in compliance with the applicable regulatory requirements.

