4. STUDY DESIGN

4.1 General Description

This is an observational, multicenter and cross-sectional study in NVAF elderly patients currently on NOAC treatment for their stroke prevention.

AF is classified as non-valvular AF in the absence of mitral stenosis or cardiac valvular prosthesis, since NOACs are not recommended for patients with mechanical heart valve (level of evidence B) or moderate to severe mitral stenosis (level of evidence C) (3).

The study will be conducted in approximately 50 sites in Spain. Investigators from different specialties are planned to be included as follows: 35 cardiologists, 10 hematologists and 5 geriatricians.

Document:	H:\HOR-Europe\2019\2512352 - Study on anticoagulation management - BI\Proyecto\Estadística\SAP\SAP_REBELD_version1.0_08072020.docx		
Author:		Version Number:	Version 1.0
		Version Date:	[08072020]

Template No.: RWI_TP_BIOS0013 Revision 1

Reference: RWI_WI_BIOS0015

Effective Date: 15Jun2018

The design of the study imposes a single visit to be performed for the informed consent signature and data collection that will coincide with one of those performed by the patients as part of routine follow-up of their disease, without interfering with usual clinical practice of the investigator.

A specific therapeutic strategy has already been assigned to each included patient, based on routine practice and without interference with the physician's prescription habits. The observational nature of the study is ensured as no diagnostic or therapeutic intervention outside of routine clinical practice will be applied.

Cardiology, hematology, geriatric services at a hospital setting, specialty medical offices and nursing homes, who regularly prescribe NOACs for stroke prevention in NVAF patients may be invited to participate.

The number of patients per site to be included in the study will be initially set up to a maximum of 10 patients per site. Once the 50% of the participating sites have been initiated, the recruitment will become competitive until the end of the study and the limitation of 10 patients per site will be removed to allow sites to continue with the recruitment.

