14.3.3 Clinical Frailty Scale

Clinical Frailty Scale grading at the time of the study visit by current NOAC type will be described as the number of patients on each category of frailty as evaluated by the investigator according to patient's records. In addition, CFS score will be summarized in the following two categories: Frailty patients (CFS scoring >4) and Non-frailty patients (CFS scoring ≤ 4).

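### The exploratory frailty regression pools about 50 sites with no site term, so its odds ratio can mix between-site with within-site association; a site-stratified model beside it would show whether it does

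*SAP*

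**What the plan says.** The model is in SAP 14.6: "Multivariate logistic regression will be used to evaluate the association between the Clinical Frailty Scale", split at CFS above 4, and thromboembolic and bleeding events that followed the start of anticoagulation. The candidate covariates are given as "Other factors will be age, sex, BMI, smoking habit, alcohol consumption, time since NVAf diagnosis, NVAf type, modified EHRA scale, procedures and interventions", followed by "comorbidity Charlson index and clinical risk factors". Selection is by univariate screen: "All variables which have a P value of less than 0.1 will be included in the multivariate analysis". The footnote to Table 53 repeats the list, and the table reports an estimate, standard error, p-value and odds ratio. SAP Table 11 shows what the clinical risk factors are: heart failure, NYHA class, LVEF, coronary disease, sleep apnoea, hypertension and hyperlipidemia.

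The list has no site, specialty or type of centre. Neither document mentions a random effect, stratification by site, GEE or a cluster-robust variance. SAP 8.1 rules out statistical methods for handling bias.

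On the data, SAP 14.3.3 describes the CFS category "as evaluated by the investigator". Protocol 9.10.2.1 lets that score go straight into the eCRF without a source document. Protocol Table 3 takes the event history from medical records. Protocol 9.1 states: "The study will be conducted in approximately 50 sites in Spain". SAP 4.1 plans "35 cardiologists, 10 hematologists and 5 geriatricians". Protocol 9.2.1 names the settings that may be invited: "Cardiology, hematology, geriatric services at a hospital setting, specialty medical offices and nursing homes". Under Protocol 9.2 the limit of 10 patients per site is lifted once half the sites have been initiated.

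SAP 4.6 lists the model as an addition to the protocol. SAP 8.2 and 8.3 say that there will be no statistical test and no modelling, which contradicts 14.6.

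**The concern.** The outcome (a judgement grade) and the explanatory variable (charted events) are both produced at the same site. Sites may differ in how frail their patients are or how strictly they grade them. They may also differ in how often events happen or how fully they are recorded. If the two differences run together, patients at some sites will be both graded frail and recorded as having events. A model that treats the 500 patients as one pool then shows an association even when frail and non-frail patients at the same site have the same event history.

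Age, Charlson index and risk factors can take up part of a case-mix difference. They cannot take up grading style or chart completeness. Because the screen draws only on listed variables, site cannot enter later. At stake is the reading of Table 53, the study's only regression: its odds ratio could be taken as a statement about patients when part of it is about sites.

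**Working it through.** **1. The plan's own figure.** The plan gives no precision or effect size for this regression. Its only precision figure is the width of the Clopper-Pearson interval at n = 500 (Protocol Table 4). With lower limit Beta(0.025; x, n-x+1) and upper limit Beta(0.975; x+1, n-x), the widths at 10/20/30/40/50% are 5.46, 7.20, 8.21, 8.77 and 8.94%. The stated values are 5.46, 7.20, 8.22, 8.76 and 8.94%, so they reproduce to within 0.01 point. They treat patients as independent and say nothing about sites. (SAP Table 1 prints 8.76% in the 50% row; that is a separate slip with no bearing here.)

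**2. The mechanism by hand.** From the documents: 500 patients and 5 of 50 investigators geriatricians, so 50 geriatric patients and 450 others at 10 per site. Assumed: frail 70% against 30%, events 30% against 15%, frailty and events independent within each group (odds ratio 1 in both).

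- Frail with event: 450×0.3×0.15 + 50×0.7×0.30 = 30.75
- Frail without event: 450×0.3×0.85 + 50×0.7×0.70 = 139.25
- Non-frail with event: 450×0.7×0.15 + 50×0.3×0.30 = 51.75
- Non-frail without event: 450×0.7×0.85 + 50×0.3×0.70 = 278.25

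Pooled odds ratio = (30.75×278.25)/(139.25×51.75) = 1.19. If the geriatric event rate is instead lower (12% against 25%), the same sum gives (37.95×249.45)/(132.05×80.55) = 0.89. If only frailty differs, it is exactly 1. So the shift can go either way, and it needs a difference in both.

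**3. Variation between sites.** For site j: logit P(frail) = a + 0.9u_j and logit P(event) = b + 0.6v_j, with corr(u, v) = ρ and no association within any site. There are 50 unequal sites, 500 patients, about 30% frail, about 17% with an event, and no covariates. Everything except the 500 and the 50 is assumed. The ranges cover repeat runs; rejections are at a nominal 5%.

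| ρ | Pooled odds ratio | Pooled rejections |
|---|---|---|
| 0 | about 1.0 | 6% |
| 0.3 | 1.12-1.13 | 8-10% |
| 0.5 | 1.21-1.22 | 13-15% |
| 0.8 | 1.40-1.41 | 28-29% |

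Stratified by site, the odds ratio is 0.98-1.00 with 4-6% rejections.

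**4. Is a specialty term enough?** This uses 35/10/5 sites of 10 patients and 1,000 datasets per row, with a simulation error of about 0.7 points (√(0.05×0.95/1000)). The last three columns are rejection rates.

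| Assumed site differences | Pooled odds ratio | No site or specialty term | Specialty added | Stratified by site |
|---|---|---|---|---|
| By specialty only, as in step 2 | 1.18 | 8.5% | 3.7% | 3.8% |
| Same, plus site SDs 0.6 and 0.5, ρ = 0.3 | 1.25 | 16.8% | 7.1% | 4.7% |
| No specialty effect, site SDs 0.9 and 0.7, ρ = 0.5 | 1.27 | 18.5% | 17.9% | 5.0% |
| Geriatric events lower | 0.87 | 7.7% | 3.7% | 3.4% |
| Frailty differs by specialty, events equal | 0.99 | 5.4% | 5.8% | 5.9% |
| Independent site effects | 1.00 | 5.2% | 4.9% | 4.7% |

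A specialty term is enough only when the differences follow specialty.

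**5. Cost and fallback.** In the step 3 setting, about 25-27% of patients sit in sites with no variation in frailty or in events and do not inform the stratified event odds ratio. Its standard error was about 6-18% larger across runs. A random site intercept left odds ratios of about 1.04 / 1.08 / 1.15 at ρ = 0.3 / 0.5 / 0.8, so it removes the shift only in part.

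**The case against.** The strongest reply is that every size above is assumed. No document gives a between-site spread for frailty or events, or a correlation between them. At zero correlation there is no shift, and the listed covariates, absent from the simulations, would absorb some of it. This stands: a reader might take 1.4 and 29% as what to expect here, but they are the far end of an assumed range. SAP 14.6 also sets no 5% decision rule for this model, so the rejection rates are only a yardstick.

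Second, pooled does not mean wrong. The study is descriptive and Protocol 9.2.1 seeks national representativeness. If some sites truly have frailer patients with more events, the pooled association is a real feature of that population. Only grading style and recording are artefacts, and the simulations do not separate them from case mix. This also stands, so the documents do not support replacing the pooled model as the main analysis.

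Third, some tempting premises go beyond the text. It is tempting to infer that each investigator grades alone, because about 50 investigators match about 50 sites. The documents describe no second or central rater, but they do not say so either, and the CFS descriptors in Protocol Annex 3 limit differences between raters. Nursing homes may be invited; no share is given.

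What remains is the omission itself: neither document supplies a site term or any clustering method for this model.

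**Conclusion.** The point holds in a limited form. The planned model cannot tell a patient-level association from one that arises between sites, and the design gives sites room to differ in both outcome and events. Whether they do, and in which direction, is unknown from the documents. A reader might infer that the reported odds ratio will be spurious or inflated. That is not supported: the shift needs correlated site differences in both variables, can be below 1, and may partly be genuine case mix.

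The illustrative size is an odds ratio of about 1.0 to 1.4 where the within-site value is 1. It rests on the assumed site standard deviations of 0.9 and 0.6, correlations from 0 to 0.8, and no covariates. Severity is minor: the model is exploratory, it serves no primary or secondary objective, and the primary outcome is unaffected.

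**What to change.** In SAP 14.6 and Table 53, report next to the pooled model a logistic regression stratified by site (conditional logistic, STRATA site in SAS). State that site is exempt from the univariate P<0.1 screen. Interpret the association as patient-level only if the two odds ratios agree; if they differ, say that part of the association lies between sites.

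If too few sites are informative and a random site intercept is used instead, force in investigator specialty and state that this removes between-site confounding only in part.

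Reconcile SAP 8.2 and 8.3 with 14.6 first, since as written they exclude the model altogether.

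The cost is a few sentences, one further model and an added block in Table 53; no new data are needed. The downside is precision. Sites without variation in frailty or in events contribute nothing to the stratified event estimate (about a quarter of patients in simulation), and its standard error is roughly 10-15% larger. That is for a single event indicator at about 17%; if rarer event types are entered separately, more sites will be uninformative.
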